The improvement in neurodevelopmental outcome we reported was primarily due to a decrease in the risk of *cognitive* impairment, measured with the Bayley scales of Infant Development, a standardized tool for assessing neurodevelopmental outcome in this age group. As mentioned above, the initial hypothesis of the study was that iNO therapy would decrease the incidence of death and chronic lung disease. However, we found that the beneficial effect of iNO therapy on neurodevelopment was independent of important clinical factors known to affect neurodevelopmental outcome, including whether infants had chronic lung disease. Furthermore, the magnitude of improvement in neurodevelopmental outcome persisted after statistical adjustment for the presence and absence of intraventricular brain hemorrhage or periventricular leukomalacia (PVL, a softening of the white matter of the brain, due to reduced blood flow). Therefore, iNO therapy appears to be directly neuroprotective in ventilated, preterm infants. The number of children in each group having cerebral palsy, motor delay, blindness, or deafness did not differ between iNO- and placebo-treated infants.

Advances in neonatal intensive care medicine notwithstanding, we have not successfully developed neuroprotective therapies for these at risk preterm infants; iNO therapy, therefore, constitutes the first

intervention to allow the preterm brain to develop normally outside the womb. In our previous study, we treated babies for one week regardless of their level of prematurity. However, we do not know what duration of treatment will result in maximum neuroprotection, and will give the best neurodevelopmental outcome to the most infants. It is likely that maximal benefit of iNO therapy will occur with longer treatment, throughout the preterm period. *Our goal, therefore, is to determine whether iNO therapy given during throughout the preterm period results in further improved neurodevelopmental outcomes, and to understand the biological relationships between iNO treatment and neurodevelopmental outcome.* To achieve this goal, we propose performing a randomized, placebo-controlled, double-blind study of the effect of iNO therapy with gestational age-determined treatment length on neurodevelopmental and growth outcomes of preterm infants. Our Specific Aims are:

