We then followed these infants after discharge for two years. We were able to maintain contact with 82% of those in the original study, a very high follow up rate for this population. In the follow-up study we found that iNO treated infants had decreased abnormal neurodevelopmental outcomes compared with placebo-treated infants. That beneficial effect persisted after statistical adjustment of the outcome for the presence of independent factors known to affect neurodevelopmental outcome: birth weight, gender, exposure to postnatal steroids, as well as factors that mediate abnormal neurodevelopmental outcome – intraventricular hemorrhage/PVL and incidence of chronic lung disease. We were able to conclude, therefore, that iNO has a beneficial, independent effect on neurodevelopmental outcome. We also found that iNO-treated infants grew better. They were only 0.5 standard deviations below the mean of full-term children, compared with more than 1 standard deviation for placebo-treated children.

There have been two other large placebo-controlled, randomized, double blind studies of iNO therapy in premature infants. In a multi-center trial, Kinsella and colleagues at the University of Colorado randomized 793 infants at 34 weeks gestation or less requiring mechanical ventilation to receive 5 ppm of iNO for 3 weeks. They reported no difference in BPD in the overall cohort. However, infants weighing 1000-1250g who received

Principal Investigator: [name]

iNO had a significantly reduced incidence of chronic lung disease compared with the placebo-treated group. Most excitingly, for the entire cohort, the incidence of the combined end point of IVH, PVL and ventriculomegaly (all signs of brain injury) was significantly reduced in iNO treated group over the placebo-treated group. This study provides support for our single center study that iNO therapy reduces overall risk of brain injury. It is also of importance to note that iNO was given for periods up to three times as long as our study, and without any adverse outcome.

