(ix) *Sample size.* In our previous study of infants with RDS, iNO treatment cut the risk of abnormal neurodevelopmental outcome by half. The baseline incidence of abnormal neurodevelopmental outcome is 40% in this age group by published NICHD data. Therefore to see a decrease of abnormal neurodevelopmental outcome to 20% (half of baseline incidence) with 80% power, 82 babies are needed in each arm of the study, for a total of 164 babies. We have previously published an overall mortality rate for intubated infants < 2000g in our nursery of 23%. Because we are including non-intubated infants, we

estimate a mortality rate of about 18%. Therefore, to ensure sufficient infants surviving to follow up, we anticipate needing to enroll approximately 215 babies over 18 months. With a historic 80% follow-up rate, we will need a total of 268 infants. Every year we admit approximately 175-200 infants with birth weights < 1500g. We therefore anticipate enrollment taking as long as 18 months. Our non-consent rate historically is < 10%.

(x) *Standards of neonatal intensive care.* Because we have shown no effect of ventilatory strategy on neurodevelopmental outcome, there will be no external control of ventilatory modality. Because this is a single-site study, variability in practice exists only between our eight member group of neonatologists, with constant care provided by nurse practitioners, residents, and nursing staff.

(xi) *Safety monitoring.* As per our clinical routine, methemoglobin is regularly monitored with arterial blood gases. Although we and others have shown that iNO therapy is safely used in preterm infants, interim safety analyses will be performed when 50% of patients enrolled. Deaths will be compared, as will the incidence of severe intraventricular hemorrhage, and tests of significance made with Chi-square. The study will be stopped if the incidence of either index in the iNO groups is significantly higher than in placebo groups.

(xii) *Primary Outcome.* As we have published, we will measure abnormal neurodevelopmental outcome at 18 months corrected age. Three disability levels will be assessed: disability (cerebral palsy, blind in both eyes, or deaf in both ears); delay (score on Mental or Psychomotor Developmental Index of the Bayley Scales of Infant Development < 70 without a disability) or normal (without disability or delay).

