(xiii) *Secondary Outcomes.* Other neurodevelopmental outcomes to be measured include the incidences of disability or delay; mean cognitive (MDI) and psychomotor (PDI) function scores will be obtained and infant growth charted. Important clinical diagnoses known to affect the risk of adverse neurodevelopmental outcomes will be tracked: respiratory distress syndrome, bronchopulmonary dysplasia, necrotizing enterocolitis, intraventricular hemorrhage (with grade), periventricular leukomalacia, retinopathy of prematurity, and failed hearing screen. Finally, detailed clinical data will be tracked on a daily basis, including fluids, ventilatory status, blood gases, feedings, etc.

(xiv) *Measures to ensure long-term neurodevelopmental follow-up.* The very high follow-up rates we have previously published require intensive efforts of a number of teams following a patient's discharge, including social services and the research staff. All preterm infants will be followed in our high risk follow-up clinic. This clinic is unusual, in that it provides routine, well-child care to its babies, as well as subspecialty care and neurodevelopmental care. Providing routine care provides an important incentive to parents to come to clinic, since they only have one appointment to make. In addition, we provide regular reminders of the role of the University of Chicago Medical Center in the lives of our families: patients receive holiday and birthday cards, and personalized invitations to our regular patient reunions. Finally, families who come for follow-up visits are given gifts and their travel expenses are reimbursed. Families are rewarded at a 9 month follow-up visit and at the 18 month follow-up visit. With this approach, our drop-out rate is less than 15% -- very low for this population by published reports.

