(xv) *Assessment of neurodevelopmental outcome.* As we have previously published, at 18 months post conceptional age, developmental screening with Bayley exams will be performed in our High Risk Follow-up Clinic by [name], who will also perform neurological examinations to identify those infants with cerebral palsy. Other assessments will include measurements of physical growth and review of routine visual and hearing examinations to determine blindness or deafness. Questionnaires assessing socioeconomic status and self report of racial ethnicity will be administered. All examiners will be unaware of treatment regimen assignment. In our previous studies, our follow-up rate of >80% is very high by published standards, especially for an inner city community such as we serve. We anticipate that rate will continue for the current study.

(xvi) *Data analysis.* As we have previously published, data will be analyzed as "Intent to Treat." . Clinical and demographic variables between groups will be compared with Fisher's exact test for categorical variables and Wilcoxon rank-sum tests for continuous variables. Primary outcomes will be analyzed with generalized linear models to obtain relative risks of primary outcome in the two groups. Effects of potential confounders will be adjusted for in the model: birth weight, sex, socioeconomic status, as well as for potential the intermediate variables: prolonged exposure to postnatal steroids, presence of chronic lung disease, severe IVH, or periventricular leukomalacia (PVL). Further analyses of Bayley scores, both cognitive (MDI) and psychomotor (PDI) will be performed.

(xvii) *Anticipated results and critique.* We anticipate that infants treated with iNO will demonstrate significantly decreased incidences of abnormal neurodevelopmental outcomes and will also demonstrate significantly increased cognitive abilities, as demonstrated by MDI scores. We further anticipate that these effects will persist after statistical adjustment for factors independently predisposing to abnormal neurodevelopmental outcome, such as male gender and gestational age, as well as adjustment for factors potentially mediating adverse neurodevelopmental outcome, such as chronic lung disease, intraventricular hemorrhage, or PVL.

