### **Specific Aim #2. Assess the mechanisms by which iNO therapy alters neurodevelopmental outcome in preterm infants.**

(i) *Rationale.* We have previously found that iNO therapy reduces the risk of abnormal neurodevelopmental outcomes independently of the level of prematurity or complications of prematurity known to affect neurodevelopmental outcome. Therefore, it appears that iNO has direct, beneficial effects on the preterm brain and its response to the stress of existence outside the womb. Previously, iNO was believed to be inactivated in the blood vessels in the lung, by binding to hemoglobin in the blood. However, there is increasing evidence that hemoglobin binding does not inactivate NO permanently, but rather transports it for delivery to target tissues. The goal of this Specific Aim, therefore, is to assess the amount of delivered NO that is transported to our patients' tissues, measure the amount of NO activity in our patients' blood, and examine the relationships between these measures, the iNO concentrations administered, and the patients' neurodevelopmental outcomes.

(ii) *Study Design.* Measurements of nitrosylated hemoglobin from arterial and venous blood samples will be made on each patient at defined points during the hospitalization: in the first 48 hrs following initiation of study gas (iNO or placebo), after 1 week of treatment, after 2 weeks of treatment. In infants who are treated longer than 2 weeks (anticipated to be all infants born before 31 weeks gestation, since they will likely still require some respiratory support), weekly measurements of venous nitrosylated hemoglobin will be made. Cyclic GMP will be measured once, after 1 week of therapy. For each patient, arterial and venous values will be compared, to identify the amount of NO that is delivered to tissues, and these values plotted over time. Mean delivered amounts will be compared across treatment groups, and individual values correlated with neurodevelopmental outcome. Cyclic GMP levels, a measure of nitric oxide activity, will be averaged within groups and treatment groups compared.

(iii) *Source of blood.* This protocol does not require for blood draws outside the regular scope of practice. Samples will be taken from regularly scheduled arterial and venous draws, and leftovers from these samples used.

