## Appendices

### A. Project schedule/Timeline of events

Time	Project Stage	Activity
Year 1 month 1	Begin patient enrollment	randomize to NO or placebo
	Begin assessment of NO delivery and metabolism during hospitalization	measurement of arterial and venous nitrite and nitrosylated hemoglobin
year 1 month 3	anticipate 1st discharges to home - assess complications of prematurity potentially affecting neurodevelopmental outcome	Routine head ultrasounds Routine head MRI at discharge Classification of chronic lung disease
year 1 month 9	Interim safety analysis	Comparison of death rates and rates of Grade IV IVH between groups
Year 2 month 7	End patient enrollment	
	Begin assessment of 18 month neurodevelopmental outcome	Bayley scales Neurologic exam Assessment of CP status Assessment of Blindness Assessment of hearing
Year 2 month 7		
Year 3 month 12	End 18 month neurodevelopmental outcome assessment	

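### An iNO effect that persists after adjustment for yes/no injury diagnoses does not establish a direct effect on the brain, and the plan does not limit the conclusion

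*Combined protocol and SAP*

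**What the plan says.** All places are in the combined protocol and SAP.

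- **Specific Aims, Aim #1** commits the trial to a statistical assessment of the roles of mediating variables.
- **Research Plan, Aim #1 (xvi)** gives the only method: a generalized linear model for the relative risk. It is adjusted for birth weight, sex and socioeconomic status, and also for intermediates: prolonged steroid exposure and "presence of chronic lung disease, severe IVH, or periventricular leukomalacia (PVL").
- **Aim #1 (xvii)** expects the effect to remain after "adjustment for factors potentially mediating adverse neurodevelopmental outcome, such as chronic lung disease, intraventricular hemorrhage, or PVL".
- **How persistence was read in the previous study.** Specific Aims: "Therefore, iNO therapy appears to be directly neuroprotective in ventilated, preterm infants". Background, section 3: "We were able to conclude, therefore, that iNO has a beneficial, independent effect on neurodevelopmental outcome". Aim #2 (i), Rationale: "it appears that iNO has direct, beneficial effects on the preterm brain".
- **Finer data.** Aim #1 (xiii) tracks "intraventricular hemorrhage (with grade"). Appendix A lists "Classification of chronic lung disease" around discharge.

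The plan does not estimate direct and indirect effects, does not address mediator error or mediator-outcome confounding, and does not say what may be concluded if the effect persists.

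**The concern.** The adjusted model asks whether the arms differ among infants with the same yes/no diagnoses. The mechanistic question is whether iNO does anything for the brain other than by reducing brain or lung injury. The two coincide only if the diagnoses capture all of the relevant injury without error, and nothing unmeasured causes both injury and outcome.

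A yes/no diagnosis blocks only the part of the indirect path that crosses its cut-off. If iNO also makes injury milder on either side of the cut-off, that part stays in the treatment coefficient and looks like a direct effect. A shared unmeasured cause of injury and outcome adds a further bias, because the adjustment conditions on something that happened after randomization.

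At stake is the mechanistic conclusion. The trial could report protection independent of IVH, PVL and chronic lung disease when iNO works wholly by reducing them. The rationale for Aim #2 starts from that same inference.

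**Working it through.** **Inputs from the documents.** Aim #1 (ix): "The baseline incidence of abnormal neurodevelopmental outcome is 40% in this age group"; 20% with iNO; 80% power; 82 per arm. Aim #1 (xvi): relative-risk GLM with presence/absence intermediates. Background, section 3 says iNO markedly reduced serious IVH and PVL in the previous trial, but gives no rates.

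**Inputs assumed.** Two-sided 5% level (not stated). Also injury rates, the strength of the severity-outcome link and diagnostic accuracy, none of which the documents give. Birth weight, sex, socioeconomic status and steroids were not simulated.

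**Step 1: the plan's own figure.** n = [1.96·√(2·0.30·0.70) + 0.8416·√(0.40·0.60 + 0.20·0.80)]² / 0.20² = (1.270 + 0.532)² / 0.04 = 81.2, so 82 per arm. This matches (ix).

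**Step 2: events.** 82 × 0.40 + 82 × 0.20 = 32.8 + 16.4, about 49.

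**Step 3: zero direct effect, all three injuries carrying the effect.** Each injury has a normal latent severity, and the diagnosis is severity above a cut-off. The outcome is abnormal when r·S + √(1−r²)·e > z(0.60), where S is the standardized sum of severities and e is standard normal noise. iNO only lowers severity.

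- Shift needed for 40% to 20%: z(0.80) − z(0.60) = 0.8416 − 0.2533 = 0.588.
- With severity correlation 0.3 and r = 0.75, the sum has SD √(3 + 6·0.3) = 2.191. The shift per injury is (0.588/0.75)·(2.191/3) = 0.573 SD.
- With placebo rates of 20%/10%/50% for severe IVH/PVL/chronic lung disease, iNO rates are 1−Φ(0.842+0.573) = 8%, 1−Φ(1.282+0.573) = 3% and 1−Φ(0.573) = 28%.

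The model is a log-link Poisson GLM with robust standard errors, fitted to treatment plus the three yes/no diagnoses, with 2,000-3,000 trials per scenario. The nominal rejection rate is 5% and the true direct relative risk (RR) is 1.

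| Scenario, 82 per arm | Adjusted arm term significant | Adjusted RR |
|---|---|---|
| Base case above | 20% | 0.72 |
| Severities uncorrelated, r = 0.75 | 30% | 0.68 |
| Lower injury rates (12%/5%/40%) | 30% | 0.68 |
| All three-injury severity scenarios | 14-33% | 0.68-0.81 |
| Only IVH/PVL severity carries the effect | 40-48% | 0.62-0.64 |

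**Step 4: a second severity model.** One brain-injury severity (with lung severity added in some runs), outcome logistic in severity, no treatment term, 1,000-1,500 trials per scenario.

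| Scenario | Yes/no diagnoses | Graded injury |
|---|---|---|
| Severe injury 20%, outcome slope 1.5-2 | 35-40% | 11-13% |
| Severe injury 20%, slope 3 | 31% | 8% |
| Severe injury 10% | 56% | 38% |
| Severe injury 30% | 19% | 5% |
| Brain and lung both mediating | 27-37% | 11-19% |

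The adjusted RR averaged 0.56-0.73 with yes/no diagnoses and 0.63-0.92 with grades. Adjusting for true severity gave 4-5%.

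**Step 5: where the result changes.** In every row the true direct effect is zero.

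| Scenario | Adjusted arm term significant |
|---|---|
| Injuries truly yes/no, measured without error | 4-6% |
| Injuries truly yes/no, misclassified (sensitivity 0.5-0.8, specificity 0.90-0.95) | 23-36% |
| Step 3 base case plus an unmeasured cause of injury and outcome, weak to strong | 13% down to 5% |

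**Step 6: does movement of the RR identify the cause?** Two comparisons were run, replacing yes/no diagnoses with grades. With zero direct effect, the RR moved from 0.61 to 0.74 and from 0.64 to 0.77. With a genuine direct effect plus mediator-outcome confounding, it moved from 0.62 to 0.72 and from 0.64 to 0.79. The patterns cannot be told apart.

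**The case against.** A reader might infer that the plan contains a mediation test that often rejects falsely. The documents do not support that. Section (xvii) states an expectation, with no test, threshold or decision rule. The language of directness describes the previous study, and is hedged in Specific Aims and in Aim #2. Aim #2 also rests on separate evidence about hemoglobin transport. The sentence in (xvii) names intraventricular hemorrhage without restricting it to severe; only (xvi) does so. The corroboration described under Expected Impact concerns the effect on neurodevelopment, not its directness.

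Nor do the documents support 'often'. They give no injury rates, injury-outcome associations or diagnostic accuracy. The 56% comes from one scenario with 10% severe injury, and in every other setting most simulated trials did not reject. One base case in the second model needs iNO to cut severe injury from 20% to about 4% (a shift of 0.89 SD), for which there is no figure in the documents.

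A reader might also infer that a large move of the relative risk toward 1, once grades are used, proves that coarse coding produced the persistence. Step 6 shows that it does not. Finer conditioning on a post-randomization variable can also increase confounding bias.

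What stands against the plan is narrower. Presence/absence adjustment is the only mediation method, the documents have already read persistence as a direct effect, and nothing prevents the same reading here. Offsetting confounding would not make the inference valid; it would only happen to cancel an error.

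**Conclusion.** The concern holds in a limited form. Persistence after adjustment for yes/no diagnoses is compatible with a direct effect, with coarse or misclassified mediators, and with unmeasured mediator-outcome confounding. It cannot separate them. With no direct effect at all, the chance of a significant adjusted effect runs from about 5% to 56%, depending on assumptions that the documents cannot settle.

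Grades reduce the error under the second severity model but do not remove it: false persistence still reached 38% in one scenario. The limit on the conclusion is therefore the essential change, and graded coding is a useful addition. The point concerns the mechanistic claim from a secondary model.

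**What to change.** 1. **In (xvii), limit the conclusion.** State that a persisting effect will be reported as 'not explained by the measured IVH, PVL and chronic lung disease' and will not be taken as evidence of a direct or independent effect. Name the reasons: coarse or misclassified mediators, and unmeasured causes of both mediator and outcome.
2. **In (xvi), for the secondary mediator-adjusted model only,** enter IVH by the grade already recorded under (xiii), for example as one ordinal term. Enter chronic lung disease by its Appendix A classification if that classification is graded; the entry does not say. Show this model beside the yes/no version, as description only. The discharge MRI is best left out, since no scoring is described.

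The cost is one or two more parameters in a secondary model with about 49 expected events, plus a more modest mechanistic claim. No new data are needed.

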### **Specific Aim #2. Assess the mechanisms by which iNO therapy alters neurodevelopmental outcome in preterm infants.**

(i) *Rationale.* We have previously found that iNO therapy reduces the risk of abnormal neurodevelopmental outcomes independently of the level of prematurity or complications of prematurity known to affect neurodevelopmental outcome. Therefore, it appears that iNO has direct, beneficial effects on the preterm brain and its response to the stress of existence outside the womb. Previously, iNO was believed to be inactivated in the blood vessels in the lung, by binding to hemoglobin in the blood. However, there is increasing evidence that hemoglobin binding does not inactivate NO permanently, but rather transports it for delivery to target tissues. The goal of this Specific Aim, therefore, is to assess the amount of delivered NO that is transported to our patients' tissues, measure the amount of NO activity in our patients' blood, and examine the relationships between these measures, the iNO concentrations administered, and the patients' neurodevelopmental outcomes.

(ii) *Study Design.* Measurements of nitrosylated hemoglobin from arterial and venous blood samples will be made on each patient at defined points during the hospitalization: in the first 48 hrs following initiation of study gas (iNO or placebo), after 1 week of treatment, after 2 weeks of treatment. In infants who are treated longer than 2 weeks (anticipated to be all infants born before 31 weeks gestation, since they will likely still require some respiratory support), weekly measurements of venous nitrosylated hemoglobin will be made. Cyclic GMP will be measured once, after 1 week of therapy. For each patient, arterial and venous values will be compared, to identify the amount of NO that is delivered to tissues, and these values plotted over time. Mean delivered amounts will be compared across treatment groups, and individual values correlated with neurodevelopmental outcome. Cyclic GMP levels, a measure of nitric oxide activity, will be averaged within groups and treatment groups compared.

(iii) *Source of blood.* This protocol does not require for blood draws outside the regular scope of practice. Samples will be taken from regularly scheduled arterial and venous draws, and leftovers from these samples used.

(iv) *Measurement of nitrosylated hemoglobin.* The S-nitrosylated hemoglobin will be measured using chemiluminescence, a technique we have used previously in the measurement of inhaled NO in tracheal air. Analysis will be performed according to published methods. Briefly, leftover blood from routine blood draws (arterial and venous) will be placed into EDTA collection tubes and taken to the lab, and centrifuged at 750xg for 5 min. Aliquots of plasma will be taken and stored at -80° for assays of nitrite and cGMP (see below). The red blood cell pellet will be removed, washed, flash-frozen on dry ice and stored at -80° C in a laboratory freezer. At the time of assay, the pellet will be rapidly thawed and pretreated with a 100-fold excess of KCN and K3Fe(CN)6, to remove NO from heme while preserving the S-nitrosothiol bond. After pretreatment (30 min), 500 µl will be passed through a Sephadex G25 column to remove contaminating nitrite and small nitrosothiols. Samples will then be reacted with I3 to release NO from S-nitroso-hemoglobin, and assayed by chemiluminescence. Results will be calibrated against S-NO-glutathione standards.

(v) *Measurement of plasma nitrite.* Plasma nitrite will be measured using a commercially available kit (World Precision Instruments, Sarasota, FL) and a spectrophotometer, available in the laboratory. A colorimetric reaction is generated, and the absorbance is read at 540 nm.

(vi) *Measurement of cGMP.* Guanosine 3'-5' cyclic monophosphate will be measured in plasma using a commercially available competitive enzyme immunoassay (Cayman Chemical, Ann Arbor, MI). The detection limit of this assay is about 6 pmol/ml, but acylation of the standards and samples will increase the sensitivity by 10-fold. Plasma proteins will be precipitated with ethanol and removed by centrifugation. The supernatant will be dried under nitrogen and re-suspended in diluted sample buffer. The assay is performed in 96-well format and after 18 hrs incubation at 4° C; Ellman's reagent is reconstituted and added to the wells. Absorbance is read 90 min later at 405 nm. Results will be calibrated against standards assayed simultaneously.

(vii) *Data Analysis.* Arterial-venous differences in S-nitroso-hemoglobin and plasma nitrite levels will be calculated on a patient-by-patient basis. Mean levels within groups will be compared across groups, and statistical significance tested with ANOVA. Individual values of A-V differences will be compared with neurodevelopmental outcome on a patient-by-patient basis and assessed with regression techniques. Similar analyses will be performed with cGMP values.

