In the laboratory component of this study, we propose to measure NO metabolites in blood in children treated with iNO or placebo, and calculate the NO delivery to tissues using arterial and venous measurements. We will describe the time course of these metabolites during the course of iNO therapy, and correlate the level of NO metabolites with neurodevelopmental outcome.

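### Aim 2 schedules no NO-metabolite sample before study gas, so the group comparison loses precision and the outcome regression cannot separate native NO from NO added by the gas

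*Combined protocol and SAP*

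**What the plan says.** Specific Aim #2, (ii) Study Design, takes arterial and venous nitrosylated hemoglobin "in the first 48 hrs following initiation of study gas (iNO or placebo), after 1 week of treatment, after 2 weeks of treatment". In infants treated for more than two weeks, "weekly measurements of venous nitrosylated hemoglobin will be made". For the second messenger, "Cyclic GMP will be measured once, after 1 week of therapy".

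Plasma nitrite has no schedule of its own. Under (iv), "Aliquots of plasma will be taken and stored at -80° for assays of nitrite and cGMP", so its timing is inferred from the shared tubes. Under (iii), "Samples will be taken from regularly scheduled arterial and venous draws, and leftovers from these samples used".

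Appendix A has only the entry "Begin assessment of NO delivery and metabolism during hospitalization", listed with the start of enrollment, and names no pre-gas sample. Background section 4 states the descriptive aim: "We will describe the time course of these metabolites during the course of iNO therapy".

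Specific Aim #2, (vii) Data Analysis, forms arterial-venous (A-V) differences in S-nitroso-hemoglobin and nitrite for each infant. Then, "Mean levels within groups will be compared across groups, and statistical significance tested with ANOVA". The individual differences are related to neurodevelopmental outcome by regression, and cGMP is handled similarly. No baseline value, change from baseline or covariate is named for Aim 2.

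**The concern.** Background section 4 recognises that the NO carried in blood is partly given and partly made by the infant. Every planned measurement is taken with study gas running, so in the iNO arm it combines the two sources. In the placebo arm it is wholly native.

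Two analyses are affected, in different ways. In the comparison of arms, differences between infants in native NO add to the error term, and no covariate is available to remove them. In the regression on outcome, the individual metabolite values are not randomised. An infant's native NO may vary with maturity or illness, and it enters the slope alongside the NO that the gas added. This regression is the main mechanistic test of Aim 2. A pre-gas value that is not collected cannot be recovered once gas has started.

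**Working it through.** **Sampling schedule.** Setting (ii), (iii), (iv) and (vii) of Specific Aim #2 beside Background section 4 and Appendix A gives:

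- Nitrosylated hemoglobin: 0–48 h after gas starts, 1 week, 2 weeks, then weekly venous only. None before gas.
- cGMP: one sample at 1 week. None before gas.
- Nitrite: no stated times; same tubes, so by inference none before gas.

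The 0–48 h sample cannot act as a baseline in the iNO arm, because treatment is already under way. In the placebo arm it indicates native NO, but only at group level.

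**The plan's own figure.** The only sample-size calculation is for Aim 1, in Specific Aim #1 (ix): 40% versus 20%, 80% power, 82 per arm. With two-sided alpha 0.05 (assumed, as none is stated) and pooled variance:

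n = [1.96·√(2·0.3·0.7) + 0.8416·√(0.4·0.6 + 0.2·0.8)]² / 0.2² = (1.2702 + 0.5323)² / 0.04 = 81.2, rounded up to 82.

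This reproduces. Aim 2 has no stated effect size, SD, correlation or power, so what follows is illustration.

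**Group comparison.** Let r be the correlation between the pre-gas and on-gas values of the quantity analysed. Adjusting for the pre-gas value multiplies residual variance by 1 − r². With a standardised difference d and n infants per arm, power = Φ(d·√(n/2)/√(1 − r²) − 1.96). The detectable difference at 80% power is 2.80·√(2/n)·√(1 − r²) SD. Assumed inputs are r from 0.3 to 0.7; d = 0.5 with n = 60; and, separately, n = 82, as if every infant in the Aim 1 calculation had usable samples.

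| r | Variance cut, r² | Equivalent gain in n, 1/(1 − r²) | Power, 0.5 SD, 60 per arm | Detectable difference, 82 per arm | n per arm for 0.438 SD |
|---|---|---|---|---|---|
| no baseline | 0 | 1.00 | 78.2% | 0.438 SD | 82 |
| 0.3 | 9% | 1.10 | 81.9% | 0.417 SD | 75 |
| 0.5 | 25% | 1.33 | 88.5% | 0.379 SD | 62 |
| 0.7 | 49% | 1.96 | 97.0% | 0.312 SD | 42 |

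First line worked: 0.5·√30 = 2.739; 2.739 − 1.960 = 0.779; Φ(0.779) = 0.782.

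The table assumes that every infant has a baseline. If only a share p does, and the rest are kept with a missing-baseline indicator, the cut is about p·r². With p = 0.5 (assumed) it is 4.5%, 12.5% or 24.5%.

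**Change score.** With equal variances, on-gas minus pre-gas has variance 2(1 − r) times that of the on-gas value: 1.4 at r = 0.3, 1.0 at r = 0.5 and 0.6 at r = 0.7. It adds noise whenever r is below 0.5.

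**Outcome regression.** Suppose a share λ of the between-infant variance in the on-gas value is starting level, unrelated to outcome and independent of the NO added. The slope for added NO then shrinks to 1 − λ of its value: 90% at λ = 0.1, 75% at 0.25 and 50% at 0.5. If starting level itself relates to outcome, the slope is confounded, and the planned data cannot show in which direction.

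**The case against.** The strongest reply is that the design already contains two controls.

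- **The A-V difference.** It subtracts any level common to an infant's arterial and venous blood at that moment. A reader might infer that nothing in the analysis removes an infant's own level; the documents do not support that for S-nitroso-hemoglobin or nitrite. What remains is the pre-gas A-V gradient. The reply does not cover cGMP, which (ii) treats as a single level, or the venous-only weekly samples.
- **The placebo arm.** It shows native NO at the same ages. A reader might infer that the group comparison is biased. It is not: allocation is randomised within birth-weight strata, and the loss is precision only. This reply does not reach the outcome regression.

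A further reply is that total NO delivered, native and administered, is a legitimate exposure for the hypothesis in the Specific Aims. That is fair. But the rationale of Specific Aim #2 speaks of delivered NO and the concentrations administered, which leaves the exposure ambiguous. Without a pre-gas value, only one of the two readings can be examined.

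There are also limits on any remedy. Specific Aim #1 (xvii) raises the possibility that native NO production falls during prolonged iNO, so a pre-gas value need not represent native NO weeks later, and r may be low. Consent is sought before birth where possible and treatment is meant to run from birth, so the pre-gas window may be short. These points stand, and they shape the fix.

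Finally, a time course without a time zero might look like a contradiction. It is not, since Background section 4 promises only a description during therapy.

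**Conclusion.** The gap is real but limited. All scheduled nitrosylated hemoglobin and cGMP samples follow the start of gas, as by inference do those for nitrite, and no baseline covariate is available or named.

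For the group comparison the cost is precision: 9%, 25% or 49% of residual variance at r = 0.3, 0.5 or 0.7 if every infant had a baseline, and less in practice. At r = 0.3 the illustrative power gain is under four percentage points. For the outcome regression the cost is interpretation: the slope cannot be assigned to NO added by the gas. The case is strongest for cGMP and for that regression.

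A reader might also infer that a pre-gas value would isolate delivered NO and remove confounding by maturity or illness. It would do neither alone: native production may change on treatment, and confounding needs covariates. The values of r, λ, p, the effect size and the numbers sampled are all assumptions. The primary outcome is unaffected. The change is worth making because the blood source is already in the plan and the value cannot be obtained later.

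**What to change.** 1. In Specific Aim #2 (ii) and (iii), add a time-zero sample. Where routine leftover blood exists from before study gas starts, store and assay it for cGMP. Assay it for S-nitroso-hemoglobin and nitrite when both arterial and venous leftovers exist, since a baseline A-V difference needs the pair. State the nitrite sampling times.
2. In (vii), replace the ANOVA with an ANCOVA of the on-gas value on arm and pre-gas value. A missing-baseline indicator is acceptable here because arm is randomised.
3. In the regression on outcome, enter the pre-gas value as a covariate, not as a change score, together with the baseline confounders already named in Specific Aim #1 (xvi): birth weight, sex and socioeconomic status. Handle missing baselines by multiple imputation or complete cases. A missing-baseline indicator can leave residual confounding in a non-randomised regression.
4. Report how many infants in each arm have a pre-gas sample.

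The cost is one more set of assays per infant on blood already drawn, with no extra draw. Some infants, particularly those started on gas soon after birth, will have no pre-gas sample, so the realised gain will fall below the figures shown.
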